1 INTRODUCTION

The purpose of this statistical analysis plan (SAP) is to provide detailed descriptions of predefined methods to be used for efficacy and safety analyses for Protocol 1042-SE-2001. The latest version of the protocol at the time of the writing of this statistical analysis plan is Final Protocol (Amendment 3, 24 January 2019, Version 4.0).

The structure and content of this SAP provides sufficient detail to meet the requirements identified by the Food and Drug Administration (FDA) and International Conference on Harmonization (ICH) of Technical Requirements for Registration of Pharmaceuticals for Human Use (ICH): Guidance on Statistical Principles in Clinical Trials.¹ All work planned and reported for this SAP will follow international accepted guidelines published by the American Statistical Association² for statistical practice.

The following documents were also considered in preparation for writing this SAP:

- International Conference on Harmonization (ICH) E3 Guideline: Structure and Content of Clinical Study Reports³
- ICH E6 Guideline on Good Clinical Practice⁴
- ICH E8 General Considerations for Clinical Trials⁵
- ICH E9 Statistical Principles for Clinical Trials⁶

The SAP is a supplement to the study protocol, which should be referred to for additional details on study design, study conduct, and other operational aspects of the study.

The original protocol included a double-blind phase which was planned after an open-label lead-in to confirm the dose selected achieved an approximately targeted plasma concentration of ganaxolone in the target population and to collect safety, efficacy, and feasibility of ganaxolone administration. This SAP supersedes the statistical considerations identified in the protocol; where considerations are substantially different. This SAP covers analysis of data collected from the open-label. The double-blind phase will now be conducted as a separate phase 3 study. Therefore, some of the analyses described in the study protocol will not be conducted. Key efficacy, safety, and pharmacokinetic data are summarized, and no formal statistical tests are performed for inference. Subjects are categorized into three cohorts based upon target dose of study medication. Cohorts are:

- Cohort 1: High (Target dose of 713 mg/day)
- Cohort 2: Medium (Target dose of 650 mg/day)
- Cohort 3: Low (Target dose of 500 mg/day)

2 STUDY OBJECTIVES

[figure not shown]
2.1 Primary Objective

- To establish that intravenous ganaxolone given concomitantly with 2nd line IV AED therapy is safe and effective in stopping status epilepticus that has already failed one 2nd line IV AED therapy and prevents escalation of treatment requiring an IV anesthetic drug (a 3rd line treatment) for seizure suppression.

2.2 Secondary Objectives

- To assess other secondary efficacy endpoints such as mortality, seizure cessation in SE subjects
- To assess the pharmacokinetics of adjunctive IV ganaxolone in SE subjects

2.3 Exploratory Objectives

3 STUDY DESIGN

For detail study design, as was originally planned, please refer to study protocol (Amendment 3, Version 4.0, 24 January 2019).

[figure not shown]
3.1 Study Design and Flow Chart

This is double-blind, randomized, placebo-controlled study to evaluate the safety, tolerability, efficacy of adjunctive IV ganaxolone in subjects with SE. This study will start with a small open-label group to confirm the dose selected will achieve an approximate targeted plasma concentration of ganaxolone in the status epilepticus (SE) population who are on concomitant medications, and to obtain a preliminary assessment of safety, efficacy and feasibility of ganaxolone administration.

As indicated in Section 1, the double-blind phase was not conducted as part of this study. The double-blind phase will be conducted as a separate phase 3 study.

[Figure 1](#) below shows originally planned study design.

Figure 1: Study Design Flow Chart

Adjunct treatment is planned to be 3- or 5-days (including an 18-hour taper).

Total subject participation is expected to be approximately 4 weeks.

3.2 Duration and Study Completion Definition

The original study was expected to be completed in 24 months.

3.3 Sites and Regions

This study was originally planned to be conducted globally, with approximately 150 sites planned to participate.

3.4 Study Population

Male or female subjects 12 years of age and older at the time of the first dose are eligible to participate in this study. Potential subjects are anticipated to be identified in the emergency department and/or hospital inpatient or intensive care units.

Each subject/parent/guardian/legally authorized representative (LAR) must participate in the informed consent process and provide written informed consent/assent before any procedures specified in the protocol are performed. Consent/assent for subjects who are known to be at risk for SE may be gained prior to a SE event.

3.5 Study Evaluation

The trial schedule of events is provided in Table 1 in [Appendix 1](#).

3.6 Blinding and Treatment Assignment

Not applicable. Only lead-in open-label phase was conducted in this study.

3.7 Allocation of Subjects to Treatment

Not applicable. Only lead-in open label phase was conducted hence there was no allocation of subjects to treatment.

3.8 Sample Size and Power

Original sample size (completed subjects = 242) was computed to provide 85% power assuming a 20% effect size. Three-hundred and twenty-eight subjects were to be screened to enroll 262 subjects, to allow for drop-out.

4 STATISTICAL METHODS

4.1 Analysis Populations

The Study populations will be defined as follows:

The **Screened Population** will consist of all subjects who have signed an informed consent.

The **Safety Population** will consist of all subjects who have received at least one dose of IV ganaxolone.

The **Pharmacokinetic Population** will consist of all subjects in the **Safety Population** for whom the primary pharmacokinetic data is available.

4.2 Endpoints

4.2.1 Primary Efficacy Endpoints

The primary efficacy endpoint is defined as the number of subjects who did not require an IV anesthetic drug (a 3rd line treatment) for SE treatment within the first 24 hours after study drug initiation.

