The first-line standard-of-care treatment for early and established SE (ESE) is parenteral benzodiazepines. A recent large-scale clinical study found that about 25% and 36% of subjects with SE did not respond to intramuscular (IM) midazolam and intravenous (IV) lorazepam, respectively. Only two-thirds of subjects with SE respond to the first treatment, and evidence shows prolonged seizures can result in permanent neuronal damage and contribute to the high morbidity and mortality associated with SE. Additionally, more than 20% of patients admitted for SE require intubation after benzodiazepine administration as first-line drug, solely for the sake of airway protection.

RSE is commonly defined as SE resistant to treatment with one first-line AED (benzodiazepines) and one second-line AED (phenytoin, phenobarbital, or valproate acid). Because SE tends to become more refractory to conventional treatment over time and with the number of pharmacologic agents used coma induction with an appropriate drug, such as barbiturates, propofol, or midazolam, is advocated after failure of second-line treatment. The use of third-line agents such as pentobarbital, midazolam, propofol, and phenobarbital usually results in iatrogenic coma, which necessitates protection of the airways by intubation and mechanical ventilation.

As the goal of RSE treatment is to abolish all clinical and electrographic epileptic activity, continuous EEG monitoring is essential for this patient population. Without continuous EEG monitoring, the response to IV treatment could be difficult to interpret, because subclinical electrographic seizure activity can be detected in up to 48% of subjects after control of convulsive SE. Burst suppression is often required in the intensive care phase of SE treatment, since RSE is associated with substantial mortality.

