#### **4.2 Exclusion Criteria**

Subjects are excluded from the study if any of the following exclusion criteria are met.

1. Life expectancy of less than 24 hours
2. Anoxic brain injury as the primary cause of SE
3. Recent (< 24 hour) traumatic brain injury as the primary cause of SE

4. Administered anesthesia (3rd line treatment; e.g., midazolam, propofol, thiopental, pentobarbital, or ketamine) at adequate doses and duration for the treatment of the current episode of SE that required the subject to be hospitalized and 5 half-lives of the agent used has not elapsed
5. Subjects who are intubated for the administration of an IV anesthetic drug (a 3rd line treatment; e.g., midazolam, propofol, thiopental, pentobarbital, or ketamine) to treat SE; subjects who are intubated for airway protection are not excluded
6. Subjects known or suspected to be pregnant upon screening
7. To the best knowledge of the investigator, has allergy to progesterone or allopregnanolone medications/supplements or has previously received ganaxolone or exogenous allopregnanolone
8. If renal impairment is suspected (eGFR  $\leq$  45 mL/min) or subject is currently on dialysis; if decision is made to start dialysis during study participation, subject is not excluded.
9. To the best knowledge of the investigator, subject has hepatic insufficiency at screening, for example alanine transferase or aspartate transferase level more than 5 times the upper limit of normal (ULN), or total bilirubin more than 2 times ULN at the screening visit
10. Subjects with a durable medical care agreement that would not allow hospital to administer their standard of care for treatment of SE
11. Subjects on an investigational drug that is not recommended by treatment guidelines are required to have a reasonable expectation that the investigational study drug has been cleared from their system, that is, that five half-lives have elapsed
12. Subjects who have a history or evidence of a medical condition that, in the investigator's judgment, would expose subject to an undue risk of a significant adverse event or interfere with assessments of safety or efficacy during the course of the study

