### **5.2.1 Permitted Treatment**

Ganaxolone IV solution will be administered as adjunctive therapy to the hospital's standard of care. Any medication classified by the hospital as per the standard of care will be acceptable. Anything outside of the standard of care should be discussed with the Medical Monitor.

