### **5.2.2 Prohibited Treatment**

As per the exclusion criterion in Section 4.2, the only allowable concurrent 2nd line IV AED therapies to treat the current episode of SE are fosphenytoin/phenytoin, valproic acid, levetiracetam, lacosamide, or brivaracetam. Administering fosphenytoin and/or phenytoin will be counted as one (1) AED. These drugs can be used alone or in combination with each other. If the subject is receiving oral AED therapy to manage a subject's chronic medical condition, for example, epilepsy, migraine, or neuropathic pain, that therapy is acceptable and should continue unchanged, if feasible and medically justified. This prophylactic treatment does not count towards the SE treatment failures required to qualify for this study. If any of these oral AED medications had to be interrupted around the time of the current SE episode, it is recommended that they would be re-started 10 hours after study drug initiation, if medically acceptable. Also, subjects who have been enrolled in another clinical study for SE are required to have a reasonable expectation that the other investigational drug has been cleared from their system, that is, that five half-lives have elapsed. Subjects on IV AEDs that are standard of care can be enrolled in the study. Subjects who have taken exogenous allopregnanolone or ganaxolone previously are not eligible for the study.

If a subject progresses at any time during the study to an IV anesthetic drug (a 3rd line treatment; e.g. midazolam, propofol, thiopental, pentobarbital, or ketamine and/or 4th line treatment; e.g., immunosuppressants, magnesium) for seizure suppression, study drug administration will be discontinued, however the subject will continue with the in-patient follow-up day and the week 2, 3, and 4 follow-up visits.

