## 9.7 Efficacy Analyses

### 9.7.1 Primary Efficacy Endpoint

The primary efficacy endpoint is defined as the number of subjects who did not require an IV anesthetic drug (a 3rd line treatment) for SE treatment within the first 24 hours after study drug initiation.

The primary efficacy analysis will be conducted over the mITT Set. The primary efficacy analysis will be conducted by using a logistic model that includes treatment group as a factor along with factors controlling for age, GCS, and history of epilepsy. One-sided tests will be performed and compared to the critical values shown in Section 9.4, thus ensuring overall 1-sided Type I error  $\leq 0.025$ .

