4.9.3 Prior and Concomitant Treatments and Procedures

Prior treatment includes all non-study treatment received within 30 days prior to the first dose of study medication. Concomitant treatment refers to all treatment taken between the date of the first dose of study medication and the last follow-up visit/contact and are recorded in eCRF pages.

Prior and concomitant medications (Non-AEDs) will be listed and summarized by group (by cohort and overall). Antiepileptic drugs (AEDs) are also collected as part of prior and concomitant treatments. A separate listing and summary table will be presented for AEDs.

Additionally, Prior and concomitant Procedures and Anesthetics will be listed and summarized by group (by cohort and overall).

Medications are coded using the WHO Drug dictionary.

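### The primary endpoint does not count an IV anesthetic given for airway sedation, and the plan has no supportive count to show how much this raises the reported success rate

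*SAP*

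**What the plan says.** **Endpoint.** SAP 4.2.1 and protocol 9.7.1 define success as not requiring an IV anesthetic, a third-line treatment, "for SE treatment within the first 24 hours after study drug initiation". The purpose of the drug is part of the definition.

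**Entry.** Protocol 4.2, exclusion 5, removes subjects intubated so that an anesthetic can be given for SE, but states that "subjects who are intubated for airway protection are not excluded". Exclusion 4 removes prior anesthetic use only if it was given "at adequate doses and duration for the treatment of the current episode of SE" and five half-lives have not passed. Adequate is not defined.

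**During treatment.** Protocol 5.2.1 says "Any medication classified by the hospital as per the standard of care will be acceptable". The stopping rule in protocol 5.2.2 is also limited by purpose: on progression to an anesthetic "for seizure suppression, study drug administration will be discontinued". The protocol's examples of third-line agents are midazolam, propofol, thiopental, pentobarbital and ketamine.

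**Analysis.** SAP 4.8 gives no derivation, table or sensitivity rule for the primary endpoint. SAP 5.1 says only that it was summarized. SAP 4.9.3 says "Prior and concomitant Procedures and Anesthetics will be listed and summarized by group", with no link to the endpoint.

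**The concern.** Propofol or midazolam given to help a subject tolerate a tube is the same drug that the protocol lists as third-line treatment for SE. A subject sedated in this way may need no anesthetic for SE because one is already running. The endpoint scores that subject as a success, and whether it does so turns on a label.

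No passage says who assigns the label, by what criterion, or how an anesthetic already running at study drug initiation is scored. Protocol 6.2.3 leaves treatment decisions to the investigator, and SAP 3.6 confirms that only the open-label phase was run. The central reader in protocol 9.9 verifies EEG patterns, not the reason for a drug. The purpose item in the SE questionnaire (protocol 7.2.2.6) asks only about AEDs not already used in the current episode.

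With no control arm and no test, the bare proportion is the efficacy result. It is meant to support the objective of preventing escalation to an IV anesthetic (SAP 2.1).

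**Working it through.** **1. Does the text allow the case?** Take a subject intubated for airway protection and sedated with propofol from hour 1.

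- Exclusion 5: not excluded.
- Protocol 5.2.1: the drug is acceptable if it is the hospital's standard of care.
- Protocol 5.2.2: the stopping rule is not triggered, because the stated purpose is not seizure suppression.
- SAP 4.2.1: a success, because the anesthetic was not for SE.

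Every step follows from the wording.

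**2. Direction.** A subject who fails the primary endpoint received an anesthetic for SE within 24 hours, and so also fails a count that ignores the reason. The reverse need not hold. The primary success count is therefore equal to or larger than the indication-free count.

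**3. The plan's own figure for this endpoint.** Protocol Table 7 gives power 0.85 for 40% against 60% with 242 subjects. Exact enumeration of the three-stage design (78, 100 and 121 per arm; one-sided critical p 0.0073, 0.0135, 0.0200; Fisher exact test) gives 0.446 + 0.257 + 0.150 = 0.853. The total and first stage agree with the table; the later stages differ by up to 4 points. The double-blind phase is now a separate study, so this figure only shows that 40% and 60% are rates the sponsor worked with.

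**4. Size in the open-label group.** Let p be the success rate with no such sedation, f the share of subjects sedated with a listed anesthetic for another reason, and n = 30 (protocol synopsis, up to approximately 30). The documents give no value of f for this population, so 5-20% is an assumption. Assume also that the sedated subjects would have had the same p, and that all are scored as successes.

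Reported rate = p + f(1 - p). Extra successes = n × f × (1 - p).

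| p | f | Reported rate | Extra successes in 30 |
|---|---|---|---|
| 0.40 | 0.05 | 0.40 + 0.05 × 0.60 = 0.43 | 0.9 |
| 0.40 | 0.10 | 0.40 + 0.10 × 0.60 = 0.46 | 1.8 |
| 0.40 | 0.20 | 0.40 + 0.20 × 0.60 = 0.52 | 3.6 |
| 0.60 | 0.05 | 0.60 + 0.05 × 0.40 = 0.62 | 0.6 |
| 0.60 | 0.10 | 0.60 + 0.10 × 0.40 = 0.64 | 1.2 |
| 0.60 | 0.20 | 0.60 + 0.20 × 0.40 = 0.68 | 2.4 |

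**5. What a second count would show.** Under the same assumptions an indication-free count gives p(1 - f). The gap between the two counts is p + f(1 - p) - p(1 - f) = f. With p = 0.40 and f = 0.20 the primary count reads 52% and the indication-free count 0.40 × 0.80 = 32%, with the true 40% between them. The two counts bracket the answer; neither corrects it alone.

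**The case against.** The strongest reply is that the purpose limit is deliberate and coherent. The objective concerns escalation to an anesthetic for seizure suppression, and the endpoint matches it. An indication-free count answers a different question and penalizes genuine airway sedation. This stands, and it is why the primary definition should stay.

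Safeguards also exist. SE must be confirmed immediately before the bolus (protocol 6.2.3 as summarized in the synopsis, and 7.1.2.1), so an agent already running had not stopped it. Exclusion 12 lets the investigator remove subjects whose condition would interfere with efficacy assessment. These help at entry but do not reach sedation started or increased afterwards. Anesthetic exposure is tabulated under SAP 4.9.3, but a reader cannot see from that which successes it belongs to.

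Three stronger readings are tempting, and the documents do not support them.

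- *Subjects on a less than adequate anesthetic for SE at entry become successes.* On the wording, an anesthetic still needed for SE after initiation is a failure. What is unsettled is residual drug, or a running agent whose stated purpose changes.
- *One subject in five is affected.* Protocol 1.1 says that "more than 20% of patients admitted for SE require intubation after benzodiazepine administration as first-line drug", solely for airway protection. That is a background statement about a first-line setting; this trial enrols after a second-line IV AED has failed. Nor does it say how many received a listed anesthetic. Taking 25-100% of 20% gives 5-20%, or 1.5 to 6 of 30, but that is an assumed number exposed. Only those who would otherwise have failed inflate the result.
- *Such sedation is usual here.* The documents permit it; they do not say how often it occurs.

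**Conclusion.** The point holds as a gap in how the endpoint is scored and reported. Success depends on the attributed purpose of a drug that is itself a listed third-line treatment, the site is unblinded, no criterion is given, and the effect on the count runs in one direction. The scoring of an anesthetic already running at initiation is also unsettled, apart from the case where it is still needed for SE.

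The size cannot be fixed from the documents. If 5-20% of subjects are sedated in this way, have the same underlying success rate as the rest, and are all scored as successes, the rate is raised by 3 to 12 points at a true 40% and by 2 to 8 points at a true 60%. If no such subject exists, it is zero.

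A reader might infer a false-positive test. That does not follow: SAP 4.8 plans no inferential test, and the SAP covers only the open-label group. The consequence is a descriptive proportion that may be too high by an amount the reader cannot see. This is a cheap improvement to the reporting and does not invalidate the endpoint.

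**What to change.** Keep the primary definition. Add to SAP 4.2.1 and 4.8:

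1. A statement of who assigns the purpose of an anesthetic, by what criterion, and how an agent running at study drug initiation is scored.
2. A pre-specified supportive count in which any listed IV anesthetic (midazolam infusion, propofol, thiopental, pentobarbital, ketamine), running at or started within 24 hours of initiation, is a non-success whatever the stated reason. Include any other agent that the primary count treats as third line, so that the ordering of the two counts holds.
3. The primary result shown separately for subjects who were intubated or on a listed anesthetic at initiation, and for the rest.
4. Both counts side by side, by cohort and overall, read as a range. The supportive count does not replace the primary one.

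The cost is SAP text and one table. Protocol 5.1, 5.2 and Table 1 note u already call for prior treatments and anesthetics to be recorded without a purpose limit. Two practical checks are needed. The documents do not show whether clock times are recorded; if only dates are, the SAP needs a stated rule for the 24-hour window. The schedule attached to the SAP has no intubation question, so intubation status may have to come from the procedures data in SAP 4.9.3. The downside is that genuine procedural or airway sedation counts as a non-success, in the supportive count only. No clinical rule changes.

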4.2.2 Secondary Endpoints

The following are secondary endpoints:

- For subjects on concomitant second-line therapy: time to cessation of SE or next treatment decision (defined as the need for an IV anesthetic drug (a 3rd line treatment) when on ganaxolone)
- Level of responsiveness as assessed by the GCS within 24 hours of SE stopping

- The number of subjects who did not require additional 2nd line IV AED therapy for SE treatment in the 24-hours after study drug taper
- Safety and tolerability of IV ganaxolone as adjunctive SE therapy as assessed by neurologic, EEG, and physical examinations, clinical laboratory tests, ECGs, vital signs, and spontaneously reported AEs
- Number of subjects who maintained SE resolution 24 hours after study drug taper and at Week 4
- Number of subjects with seizure(s) following cessation of SE through the 24-hour post-taper follow-up day
- Level of responsiveness as assessed by the GCS if SE is continuing, on the 24-hour post-taper follow-up day
- Seizure burden assessed as duration of electrographic seizure activity per hour of EEG recording collected
- Clinical outcome at the 24-hour post-taper follow-up day and Week 4
- Characterization of the pharmacokinetic profile of IV ganaxolone in SE subjects
- Length of stay in intensive care unit and hospital, mortality, and seizure freedom

